#### **Exclusion criteria**

- 1. Any associated cardiac defect except persistent left superior vena cava and coarctation of the aorta
- Any significant (i.e. that might influence outcome) extracardiac anomaly and/or known chromosomal aberration. Also, if such a condition is present at inclusion but diagnosed only after birth the case will be retrospectively excluded.

Endocardial fibroelastosis is accepted. Cases with severe mitral regurgitation and left atrial enlargement with or without restrictive or intact atrial communication and with or without hydrops will be included but analyzed as a separate group (17). Also cases with atrial septal balloon dilatation or stent placement will be included if the first intervention was aortic valvuloplasty or if no fetal aortic valvuloplasty was performed.

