#### Secondary objective

To evaluate fetal and maternal safety of fetal valvuloplasty.

Safety variables:

- Intervention-related fetal death (defined as fetal death within 24 hours of procedure).
- Fetal death not directly related to the intervention, except termination of pregnancy.
- Maternal complications to procedure (requiring intensive care or resulting in maternal death).
- Preterm delivery < 37 weeks.
- Fetal left heart growth from the point of study inclusion until just before the first postnatal catheter or surgical intervention

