2 STUDY POPULATIONS

2.1 Definition of Study Populations

2.1.1 Full Analysis Set for All Enrolled

Fetuses with severe MR and severe LA enlargement and/or intact or highly restrictive interatrial communication and/or cases with hydrops present at inclusion are all high-risk cases regarding survival, but may have a rather good prognosis if they survive the first critical period. It is likely they will be overrepresented in the FAV group to such a degree that it will be difficult to control for through propensity score matching. Therefore this subpopulation will be excluded from the full analysis set and analysed separately. Fetuses developing any of these conditions after inclusion will not be excluded from the full analysis set.

All enrolled fetuses that have satisfied inclusion/exclusion criteria and belong to FAV 1+2 and no-FAV 1+2 groups and not listed as belonging to the high-risk population described above will be included in the Full Analysis Set enrolled (FAS_{ENR}) population. Infants wrongly included in the study (not fulfilling all inclusion or fulfilling any of the exclusion criteria) will not be part of the FAS_{ENR} population, but will be described in the safety analyses. As detailed under 1.3.2, also subjects with exclusion criteria present at inclusion but diagnosed only after birth will be retrospectively excluded from the FAS_{ENR} population.

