2.1.6 Safety Population

All enrolled fetuses will be included in the safety population, also those wrongly included if such cases will exist.

Figure 5. Full analysis sets (FAS)

ToP=Termination of Pregnancy; IUD=Intrauterine Death; GW=Gestational Weeks; FAS=Full Analysis Set; FAV=Fetal Aortic Valvuloplasty

STATISTISKA KONSULTGRUPPEN	Statisti	cal Analysis Plan
Protocol: Effect of fetal aortic valvuloplasty on outcomes	Protocol No):
	Version: 1.0	Page 14 of 26

Figure 6. Per protocol populations (PP)

ToP=Termination of Pregnancy; IUD=Intrauterine Death; GW=Gestational Weeks; PP=Per Protocol; FAV=Fetal Aortic Valvuloplasty

Figure 7. Safety population

GW=Gestational Weeks; FAV=Fetal Aortic Valvuloplasty

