4.7.2 Intervention and Technical Details

Information about intervention and its technical details will be summarized on safety population per treatment groups.

Complications of fetal intervention and maternal complications 4.7.3

Data regarding complications and reasons for death will be described for safety population per treatment groups. No formal tests will be performed.

STATISTISKA KONSULTGRUPPEN	Statisti	cal Analysis Plan
Protocol: Effect of fetal aortic valvuloplasty on outcomes	Protocol No):
	Version: 1.0	Page 25 of 26

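### Safety tables pool high-risk fetuses that the SAP keeps out of the efficacy set, so the FAV versus no-FAV comparison of non-procedural fetal death is confounded by the case mix the SAP itself predicts

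*Protocol*

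**What the plan says.** **Separation of high-risk fetuses.** The protocol (Exclusion criteria) admits fetuses with severe mitral regurgitation and left atrial enlargement, and says that such cases "with or without hydrops will be included but analyzed as a separate group". SAP 2.1.1 describes a high-risk group defined at inclusion (severe mitral regurgitation with severe left atrial enlargement, an intact or highly restrictive atrial communication, or hydrops). It says that these "are all high-risk cases regarding survival" and, of their distribution between arms, "It is likely they will be overrepresented in the FAV group to such a degree that it will be difficult to control for" by propensity score matching. It concludes: "Therefore this subpopulation will be excluded from the full analysis set and analysed separately". SAP 2.1.5 defines the same group as the High-Risk Population.

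**Safety.** Fetal and maternal safety is the protocol's secondary objective, and one of its variables is "Fetal death not directly related to the intervention, except termination of pregnancy". SAP 2.1.6 sets the population: "All enrolled fetuses will be included in the safety population, also those wrongly included if such cases will exist". SAP 4.7.3 gives the analysis: "Data regarding complications and reasons for death will be described for safety population per treatment groups", without formal tests. SAP 4.7.2 and 4.7.4 likewise describe technical details and events by group. Tables 3.1 to 3.3.x, including the left heart growth models, all carry the label Safety Population, and none lists a split by risk status.

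**High-risk output.** SAP 4.6.3, under Efficacy Analyses, plans descriptive data on primary and secondary outcomes for the high-risk subgroups. These go to Tables 2.4.x, not to the safety tables.

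**The concern.** The SAP's reason for taking these fetuses out of the efficacy comparison is that they die more often and are likely to be concentrated in one arm. Fetal death is also a safety variable, so the same reason applies to the safety comparison, but there the plan does nothing about it. A higher rate of non-procedural fetal death in FAV could then reflect who was treated and not what the treatment did.

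Secondly, the death rate within 24 hours of the procedure is planned only for all enrolled fetuses. A reader who sets it beside the FAS_ENR benefit compares harm in one population with benefit in another.

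The protocol (Publication of results) allows safety and left heart growth to appear in a first, separate paper. The pooled tables could therefore be read on their own, before the 2-year outcome is available.

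**Working it through.** The plan states no figure on this point: no high-risk share by arm and no fetal death rate by risk status. The check has two parts.

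**1. Is a safety analysis by risk status or with adjustment planned anywhere?**
- SAP 2.1.6: the set is all enrolled, so high-risk fetuses are in it.
- SAP 4.7.2 to 4.7.4: description by group only.
- SAP 4.1 states generally that all analyses are adjusted for confounders. The methods it names for safety data are unadjusted two-group tests (Fisher's exact, chi-square, permutation), and SAP 4.7.3 then says there are no formal tests. No adjusted method is named for fetal death or complications.
- SAP 4.6.3: high-risk output on primary and secondary outcomes. No safety table is listed for fetuses who are not high-risk.

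**2. How large could the distortion be?** Let *b* be the fetal death rate in standard-risk fetuses, *h* the rate in high-risk fetuses, and *s* the high-risk share of an arm. If FAV has no effect, *b* and *h* are the same in both arms, and the pooled rate in an arm is *b*(1 − *s*) + *h* *s*. All inputs below are assumptions: *b* 5% or 10%, *h* 20% to 40%, *s* 20% to 40% in FAV and 5% or 10% in no-FAV.

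| *b* / *h* | *s* FAV / no-FAV | FAV | no-FAV | Difference (points) | Ratio |
|---|---|---|---|---|---|
| 10% / 30% | 20% / 5% | 14.0% | 11.0% | 3.0 | 1.27 |
| 5% / 20% | 20% / 5% | 8.0% | 5.75% | 2.25 | 1.39 |
| 5% / 30% | 20% / 5% | 10.0% | 6.25% | 3.75 | 1.60 |
| 5% / 30% | 30% / 5% | 12.5% | 6.25% | 6.25 | 2.00 |
| 10% / 40% | 40% / 5% | 22.0% | 11.5% | 10.5 | 1.91 |
| 5% / 30% | 40% / 5% | 15.0% | 6.25% | 8.75 | 2.40 |

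Third row written out: FAV 0.80 × 0.05 + 0.20 × 0.30 = 0.100; no-FAV 0.95 × 0.05 + 0.05 × 0.30 = 0.0625; ratio 0.100 / 0.0625 = 1.60.

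The spurious ratio runs from 1.27 to 2.40 and the spurious difference from 2.25 to 10.5 points. Within each risk stratum the ratio is 1.0 by construction. With equal shares (10% in both arms) the pooled ratio is also 1.0, so the distortion depends entirely on the imbalance that SAP 2.1.1 predicts.

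**The case against.** **FAS_ENR already carries related outcomes.** Survival from fetal diagnosis to live birth is a secondary variable on FAS_ENR (SAP 3.4.2), analysed with adjusted Cox models. The third test in the SAP 4.1 sequence is survival to live birth at term. Fetal death counts as failure in the primary composite. Gestational age at birth is a neonatal variable tabulated for FAS_ENR (SAP 3.2 and 4.4, Table 1.4.1). A reader might infer that harm is measured only with high-risk fetuses included; these analyses show otherwise. They do not close the gap, because none separates death within 24 hours of the procedure from other fetal death.

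**Procedural harms cannot be confounded between arms.** Procedure-related death and maternal procedural complications occur only in FAV. This stands. For them the issue is only which population the rate describes.

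**Preterm delivery.** A reader might infer that preterm rates are distorted in the same way. The documents call these fetuses high-risk for survival but do not say that they deliver earlier, so this is possible but remains inference. The same holds for any difference in procedural death by risk group.

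**The protocol is not clearly breached.** The separate-group wording can be met by the protocol's own subgroup list and SAP 4.6.3, and an all-enrolled safety set is conventional. Both points stand. The weakness is that the pooled presentation is the only one planned. It could also be argued that the secondary outcomes in SAP 4.6.3 include safety, since safety is the stated secondary objective. Even so, no safety table for fetuses who are not high-risk would follow.

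**Chance may hide or reverse the distortion.** With rates of 10.0% and 6.25% and the planned 100 and 50 fetuses, counts near 10/100 and 3/50 give a Fisher p of 0.55, and FAV would look equal or better in about 23% of samples. So the documents do not support saying that FAV must look worse, or that the safety conclusions will be wrong. The expected bias remains.

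**Conclusion.** The point holds in limited form. As planned, the between-arm comparison of non-procedural fetal death is confounded by a case-mix imbalance that the SAP expects and acts on for efficacy only. The rate of procedure-related death is not planned for the population in which benefit is measured. Left heart growth (Table 3.3.x) is also set on the pooled population with no stated split by risk status.

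The ratio of about 1.3 to 2.4 rests on assumed rates and shares and on no effect of FAV. It shows what the design permits and is not an estimate. The direction rests on two statements in SAP 2.1.1: higher risk for survival, and likely over-representation in FAV. The analyses on FAS_ENR mitigate the problem in part. The change is worth making before the tables are produced, but the point does not call the primary analysis into question.

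**What to change.** In SAP 4.7.1 to 4.7.4 and Tables 3.1 to 3.3.x:

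1. Keep the all-enrolled tables as the complete safety record.
2. Add the same variables by arm for (a) fetuses not high-risk at inclusion and (b) the High-Risk Population as defined in SAP 2.1.5. Include left heart growth.
3. State that between-arm safety comparisons are read within these strata.
4. State that harm set beside the FAS_ENR benefit is shown for that same population, together with the all-enrolled figure. Taking the safety message from the not-high-risk column alone would push events in the sickest treated fetuses into the background, so both figures are needed.
5. State that the stratified figures remain unadjusted for other confounders, such as gestational age and left heart morphology, which SAP 4.1 names as main confounders.
6. Reconcile SAP 4.1, which names tests for safety data, with SAP 4.7.3, which plans none for complications and deaths.

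The cost is SAP wording and extra table columns. The risk classification is already defined at inclusion, so no new data are needed. The downside is small counts in the high-risk columns, above all for no-FAV: 5% of 50 fetuses is two or three cases.

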## Data collection and on-line database

Collection of clinical data and echocardiographic measurements will be through Electronic Case Report Forms (eCRF) to an on-line database managed by MediCase (MediCase AB, c/o Sahlgrenska Science Park, [name], Sweden, [contact]).

MediCase is compatible with most modern web browsers, including updated versions of Chrome, Safari, Firefox and Edge. It is supposed to be compatible also with Internet Explorer but some users may experience minor problems using Internet Explorer in certain environments. Since Internet Explorer is no longer supported by Microsoft we recommend not to use it with MediCase.

For detailed descriptions of MediCase security, MediCase workflow and eCRF functionality, please see MediCase website (www.medicase.se).

## Electronic case report forms (eCRF)

There are 14 eCRF's:

1. eCRF Inclusion criteria

All inclusion and no exclusion criteria need to be satisfied for a case to be included.

2. eCRF Inclusion

Include case if inclusin/exclusion criteria satisfied.

3. eCRF Counselling on fetal aortic valvuloplasty

If councelling was performed and, if so, what the decision was.

4. eCRF Baseline fetal echo 23+0 - 31+6

The baseline fetal echo is performed between 23+0 and 31+6 weeks. If an intervention is performed, the last exam before the intervention should be used as baseline fetal echo.

5. eCRF Additional baseline fetal echo 23+0 - 31+6

In case there is a late descision to perform an intervention, after a baseline fetal echo has already been submitted, there is an option to add an additional baseline fetal echo in the system.

6. eCRF Fetal interventions

A new eCRF Fetal interventions should be added for each intervention performed.

7. eCRF Follow-up fetal echo 33+0 - 34+6

The follow-up fetal echo is performed between 33+0 and 34+6 weeks.

8. eCRF Neonatal - Birth

Gestational age and size at birth, mode of delivery and pharmacological support.

9. eCRF Neonatal - Echo

First full study after birth, and before the first postnatal intervention, surgery or cath (except emergency atrial septostomy)

10. eCRF Neonatal - Cardiac clinical diagnosis

Cardiac diagnoses before the first intervention, surgery or cath (except emergency atrial septostomy)

11. eCRF Neonatal - Neonatal discharge

Type of circulation and clinical diagnoses at discharge.

12. eCRF Follow-up at 2 years of age

Type of circulation, clinical diagnoses, pulmonary hypertension, neurological sequealae, somatic growth.

13. eCRF Postnatal procedures

All cardiac surgical and catheter interventional procedures from birth to 2 years follow-up

14. eCRF Subject termination

Reason for subject termination including completion at 2 years of age.

#### **Core laboratory**

Echocardiographic exams will be uploaded to a core laboratory FTP server managed by University of Gothenburg (IT Department, [contact]). A data transmission form (DTF) should be included with each submitted exam containing data on MediCasegenerated patient code, date of upload to server, make and model of the ultrasound machine and name of echocardiographer.

The core lab will have an audit function. Echocardiographic variables will be reported to MediCase by the submitting centre and measurements will be repeated on uploaded echoes by core lab without knowledge of submitted data. Submitted measurements differing by more than 20% from corresponding core lab measurements will be re-measured by a second reviewer, the core lab PI. If there is continued disagreement core lab will contact the submitting centre for a review of the original measurement and if this was in error the submitted value will be replaced by the core lab value provided that the image quality is acceptable. If that is not the case the value will be excluded from analysis. A similar approach will be used for variables based on qualitative or semiquantitative measurements such as magnitude of regurgitant jets on Color Doppler and ventricular function.

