#### Study design

[figure not shown]
The study is an international multicenter prospective observational cohort study with a comparison cohort. Included are fetuses with a diagnosis of aortic stenosis who satisfy inclusion/exclusion criteria between 23+0 and 31+6 weeks of gestation. The decision whether a fetal balloon dilatation shall be attempted is not part of the study protocol. The number of examinations of mother/fetus/infant in this study is not different from the number of examinations that will be recommended for someone choosing not to be part of this study. The participation in the study is not affecting the treatment mothers and fetuses are receiving during pregnancy, nor how the infant is examined and treated after birth. The aim of the study

is to, in a prospective and organized way, collect and evaluate multi-center data in order to reduce the risk for selection bias, missing data and inter-variability between participating centers.

Cases will be recruited from centers offering fetal aortic valvuloplasty and and from centers not offering this treatment. Intervention cases will be recruited from high volume intervention centers. Fetal and postnatal echocardiographic examinations will be reviewed and remeasured by a core laboratory to confirm eligibility for inclusion, and identify potential measurement errors.

[figure not shown]
Data from two fetal echoes and one postnatal will be collected and each contains a comprehensive set of two-dimensional and Doppler measurements which will enable analysis of cardiac growth and development during pregnancy. Analysis of change of dimensions of the left heart structures and selected hemodynamic variables from the point of study inclusion until just before the first postnatal catheter or surgical procedure provides an opportunity to make a comparison between the groups that is unbiased with respect to centerspecific postnatal treatment policies.

Three echocardiographic examinations and a 2-year follow-up regarding patient outcome will be performed as per Figures 1-3 below.

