1.5 Sample Size

The duration of this observational study will depend on the rate of inclusion. Based on our previous experience from a European retrospective study, and on the increasing prenatal detection rate of cardiac defects, it is estimated that 10-20 intervention cases can be included each year. Inclusion rate of non-intervention cases will depend on how many non-intervention

Protocol

Statistical Analysis Plan

Effect of fetal aortic valvuloplasty on outcomes

Version:1.0Page 11 of 26

centers decide to join the study and on the proportion of subjects offered intervention who choose to refrain. It is projected that at least half as many non-intervention cases can be included each year. The study plans to end when 100 FAV cases are enrolled and at least 50 no-FAV cases, or 5 years from the first included patient, whichever occurs first.

The power calculations below are performed applying two-sided Fisher's exact test. The main analyses, however, will require adjusted analyses due to the study design being observational and not randomized. The confounders and their relation to the outcome and the main exposure variable are not completely known at the time of the study planning. Therefore, simplified power calculations were performed in order to assure that the study has potential to answer the main posed questions.

Inclusion of 100 intervention cases and 50 controls

The aim is to include at least 100 fetuses in the FAV 1+2 groups and 50 in the comparison group no-FAV 1+2. The largest numbers will likely be in FAV 1 and no-FAV 1 while the numbers in groups FAV 2 and probably also in no-FAV 2 will be smaller.

Assuming number of fetuses included as per above, 150 in total, and 30% success rate for the primary endpoint (=transplantation-free survival from fetal diagnosis to 2 years postnatal age, having a biventricular circulation without pulmonary hypertension at that time) in the no-FAV 1+2 group and 60% success rate in the FAV 1+2 group, using alpha 0.05 and two-sided Fisher's exact test, a power of 91.8% would be able to be achieved. For a power of at least 80%, and all other assumptions unchanged, a success rate of 56% vs 30% in the FAV and no-FAV group, respectively, would be needed to be observed.

Inclusion of 100 intervention cases and 100 controls

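### The form sent with each echo names the echocardiographer and no masking to centre or arm is stated, so core-laboratory readers confirming eligibility could often infer the arm

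*Protocol*

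**What the plan says.** Protocol, Core laboratory: "A data transmission form (DTF) should be included with each submitted exam". Besides a patient code generated by the database, the form gives "date of upload to server, make and model of the ultrasound machine and name of echocardiographer". The one masking provision is that "measurements will be repeated on uploaded echoes by core lab without knowledge of submitted data". A difference above 20% leads to a second reading by the core-laboratory lead. If disagreement persists, the core laboratory contacts the submitting centre. The submitted value is replaced if it was in error and image quality is acceptable; if quality is not acceptable, the value is dropped. Qualitative and semiquantitative readings, including ventricular function, are handled in a similar way.

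Protocol, Study design (repeated in SAP 1.2): the echoes are "reviewed and remeasured by a core laboratory to confirm eligibility for inclusion, and identify potential measurement errors".

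SAP 2.1.1: "Infants wrongly included in the study (not fulfilling all inclusion or fulfilling any of the exclusion criteria) will not be part of" FAS_ENR, the set used for the confirmatory analysis.

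SAP 1.2 and 1.4: all intervention cases come from high-volume centres. No-FAV 1 comes from centres that neither perform the procedure nor refer for it. No-FAV 2 comes from performing or referring centres where the parents declined. On relative size, SAP 1.5 says: "The largest numbers will likely be in FAV 1 and no-FAV 1".

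**The concern.** The comparison is not randomised. SAP 4.1 names the strict echocardiographic inclusion criteria as the design's means of limiting bias, and the core laboratory checks those criteria. Some are sharp z-score limits. Another, depressed left ventricular function, is a qualitative judgement.

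A reader who can tell the arm may, without intending to, be stricter or more lenient in one group. Two things in the primary analysis could be affected: which fetuses stay in FAS_ENR, and the baseline dimensions that SAP 3.1 lists as potential confounders. Adjustment uses the same readings and cannot bring back a fetus that was removed. The left-heart growth comparison rests directly on these echoes, although SAP 4.1 treats it as exploratory.

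**Working it through.** No figure in the plan measures this point, and the sample size and power statements do not depend on it. The check has three steps.

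**1. How much does centre tell about arm?** Inputs: 100 FAV and 50 no-FAV (SAP 1.5) and the group definitions (SAP 1.4). Assumptions: the reader recognises the centre from the operator's name and knows its policy, and FAV cases are imaged at performing or referring centres. The no-FAV 2 share of controls, *s*, is not given. SAP 1.5 expects no-FAV 2 probably to be the smaller group, so 0% to 50% is taken as the range.

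- A centre that neither performs nor refers: no-FAV with certainty.
- A performing or referring centre: P(FAV) = 100 / (100 + 50*s*).
- Share of all arms guessed correctly: (100 + 50(1 − *s*)) / 150.
- Always guessing FAV: 100 / 150 = 67%.

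| *s* | no-FAV 2 (n) | P(FAV), performing or referring centre | Guessed correctly |
|---|---|---|---|
| 0% | 0 | 100/100 = 100% | 150/150 = 100% |
| 20% | 10 | 100/110 = 91% | 140/150 = 93% |
| 40% | 20 | 100/120 = 83% | 130/150 = 87% |
| 50% | 25 | 100/125 = 80% | 125/150 = 83% |

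Every wrong guess is a no-FAV 2 case. Centre is therefore informative but does not fix the arm. One further cue is possible: the eCRF list (Protocol, Electronic case report forms) includes an additional baseline echo for a late decision to intervene, so a second baseline exam, if uploaded, would itself point to FAV.

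**2. Where can a reader's judgement take effect?**

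- *Quantitative values.* A submitted value is replaced or dropped only after a difference above 20%, a second reading, continued disagreement and contact with the centre. Small shifts do not pass this route. The Core laboratory section does not say whose value settles eligibility when two readings differ by less than 20% but fall on opposite sides of a limit.
- *Qualitative criteria.* The approach is only said to be similar, and no trigger equivalent to 20% is given.
- *Image quality.* This ruling determines whether a disputed value is replaced or lost, and no criteria are given.

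**3. Can a size be put on it?** Not from the documents. Purely as an assumption, suppose 15% to 30% of fetuses lie within re-measurement error of a limit and knowledge of arm tips 1 in 10 of them. Of 150, that is 150 × 0.15 × 0.1 = 2.25 to 150 × 0.30 × 0.1 = 4.5 fetuses. One third are controls, so 0.75 to 1.5. Adding these as failures to the planned 15/50 (30%) gives 15/50.75 = 29.6% to 15/51.5 = 29.1%, a fall of 0.4 to 0.9 points. This ignores the 20% rule, which would reduce it further for quantitative limits.

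**The case against.** The strongest reply is that the plan already limits what one reader can do. The core laboratory has an audit role and confirms eligibility; nothing describes a single reader overruling a centre. SAP 2.1.1 removes wrongly included cases without saying that the core laboratory makes that ruling. All of this stands, and it confines the concern mainly to qualitative criteria, image quality and the confirmation of eligibility.

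Four stronger readings are tempting, and the documents do not support them.

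- *That readers are unmasked to arm.* The documents are silent. The form travels with the upload, but whether the measuring reader sees it is not stated. It lists no centre field, and a machine make and model does not identify a centre. The operator's name is the informative item. Against this, the core laboratory contacts the submitting centre in disputes, so someone there can identify it.
- *That the control rate would move by 1 to 2 points.* This needs nearly all the moved fetuses to be poor-outcome controls, although controls are a third of the sample. The rates behind it have no source in the documents.
- *That the bias could never be detected.* Submitted and core-laboratory readings both exist and can be compared by arm. SAP 2.1.1 has wrongly included cases described in the safety analyses, and SAP 4.2 counts each population by group. Those counts alone, however, would not separate core-laboratory exclusions from the planned removal of the high-risk population.
- *That the primary outcome reading is affected.* The 2-year status is recorded by eCRF, and no core-laboratory reading of it is described.

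Masking also has a limit. Technical success is defined by improved forward flow or new aortic regurgitation, so later echoes may reveal the procedure whatever the form shows.

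**Conclusion.** The point holds as a weakness in a stated procedure. The plan sends an identifier that can often reveal the arm alongside exams used to confirm entry to the confirmatory set, and the only masking it states is to submitted values. Under the assumptions in step 1, a reader who sees the form could guess 83% to 100% of arms correctly, and would be misled only for no-FAV 2.

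That range measures opportunity. It does not measure bias, and the documents support neither a magnitude for bias nor a claim that any has occurred. The possible effect on the primary analysis runs through FAS_ENR membership and baseline confounder values, and the 20% rule limits it for quantitative values. The change is worth making because it is cheap and protects the eligibility check on which a non-randomised comparison relies.

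**What to change.** Amend the Core laboratory section of the protocol as follows.

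1. What the first and second readers see carries only the study code, which should not itself reveal the centre. Operator, machine and site identifiers, including any on the images, go to the existing data management function.
2. Queries to the submitting centre pass through data management, so that neither reader deals with the centre.
3. The baseline eligibility and image-quality rulings are completed and locked without knowledge of centre, counselling decision, intervention or later echoes.
4. The SAP adds a table by arm of eligibility exclusions arising from core-laboratory review (kept apart from high-risk exclusions), replaced values and voided values.

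The cost is a revised form, a changed upload and query route, and some work to remove identifiers from images across centres. No extra reader or patient examination is needed. Follow-up and neonatal echoes may still show that FAV was done; the baseline reading is where masking is most achievable and matters most.
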